10.4 Confidentiality

To maintain subject privacy, all eCRFs, study samples, study drug accountability records, study reports and communications will identify the subject by the assigned subject identification number. The Investigator will grant monitor(s) and auditor(s) from DermBiont or designee and regulatory authority(ies) access to the subject's original medical records for verification of data gathered on the eCRFs and to audit the data collection process. The subject's confidentiality will be maintained

and will not be made publicly available to the extent permitted by the applicable laws and regulations.

All information regarding the investigational product supplied by DermBiont to the Investigator is privileged and confidential information. The Investigator agrees to use this information to accomplish the study and will not use it for other purposes without consent from DermBiont Inc. It is understood that there is an obligation to provide DermBiont with complete data obtained during the study. The information obtained from the clinical study will be used towards the development of the investigational product and may be disclosed to regulatory authority(ies), other Investigators, corporate partners, or consultants as required.

10.5 Subject Rights

Study subjects can withdraw their consent to have their clinical samples stored even after the sample has been shipped to the clinical laboratory. A study subject should contact their Investigator or the Investigator's designee and ask for his/her sample to be withdrawn from the storage and destroyed. For samples that have been partially analyzed the remaining sample will be destroyed but the clinical site and DermBiont shall be entitled to retain and use any research results obtained prior to the withdrawal of consent.

10.6 Protocol Amendments

Protocol amendments that impact subject safety, change the scope of the investigation, or affect the scientific quality of the study must be approved by the IRB/IEC and submitted to the appropriate regulatory authorities before implementation of such modifications to the study.

In the event that the protocol needs to be modified immediately to eliminate an apparent hazard to a subject, DermBiont will amend and implement the protocol change and subsequently notify the regulatory authorities and/or the IRB/IEC, as appropriate.

The Investigator must not modify the protocol without agreement from DermBiont and prior review or approval by the IRB/IEC. Any deviations from the protocol should be documented by the Investigator or designee.

10.7 Obligations of the Clinical Investigator

The Investigator will agree to be responsible for the overall conduct of the study; for completing regulatory documents and documentation of training; for ensuring that the study is conducted according to the study protocol; for protecting the rights, safety and welfare of study subjects under their care; and for insuring data quality and integrity.

If any study responsibilities are delegated, the Investigator will be responsible for maintaining written documentation of who is designate to perform the specific responsibilities.

The study will be conducted by qualified study Investigators.

The Investigator or designees are responsible for qualified subjects and collecting samples. The Investigator or designees will be responsible for maintaining records of all samples collected and investigational product administrations; recording the subject's data on the source documents and eCRFs; documenting the presence or absence of AEs following sample collection and study IP applications and following the reporting requirements of any SAEs to the Sponsor and IRB/IEC.

10.8 Institutional Review Board/Independent Ethics Committee

The Investigator must obtain written IRB/IEC approval of the protocol, approval for relevant supporting information and all types of subject recruitment and advertisement and the ICF prior to starting the study. The IRB/IEC will meet all US FDA requirements governing IRBs/IECs (21 CFR Part 56).

DermBiont or the designee must approve the ICF submitted to the investigational site's IRB/IEC. All subject recruitment and advertisements must be submitted to DermBiont or designee prior to submission to the IRB/IEC, for review.

10.9 Ethical Conduct of the Study

DermBiont and the Investigator must comply with all instructions, regulations, and agreements in this protocol and in the applicable ICH and GCP guidelines and must also conduct the study in accordance with local regulations. All protocol deviations and violations will be included in the required IEC reports in accordance with local requirements and on the appropriate forms.

10.10 Written Informed Consent

Written informed consent is required from each subject prior to any testing under this protocol, including screening tests and evaluations. The ICF, as specified by the investigational site's IRB/IEC, must follow the Protection of Human Subjects regulations listed in 21 CFR Part 50.

The background of the proposed study and the benefits and risks of the procedures and study must be explained to the subjects. It is the responsibility of the Investigator to obtain consent and to provide the subject with a copy of the signed and dated ICF. Confirmation of a subject's informed consent must also be documented in the subject's medical record prior to any testing under this protocol, including screening tests and evaluations.

All ICFs used in this study must be approved by the appropriate IRB/IEC and by DermBiont or designee. The ICF must not be altered without the prior agreement of the relevant IRB/IEC and DermBiont.

10.11 Subject Data Protection

Prior to any testing under this protocol, including screening tests and evaluations, subjects must authorize the release and use of protected health information (PHI), as described in the ICF.

11 DATA HANDLING AND RETENTION OF RECORDS

11.1 Paper and Electronic Case Report Form Completion

Paper CRF and eCRFs will be completed for each enrolled subject. It is the Investigator's responsibility to ensure the accuracy, completeness, and timeliness of the data reported in the subject's paper and eCRF. Source documentation supporting the paper and eCRF data should indicate the subject's participation in the study and should document the dates and details of study procedures, AEs, and subject status.

Investigators will maintain copies of the paper CRF and eCRFs at the clinical site. The paper CRF eCRFs will be completed as much as possible for subjects who discontinue or are terminated from the study by the investigator, and the reason for the discontinuation or termination must be clearly and concisely specified on the appropriate paper CRF and eCRF.

11.2 Retention of Records

The Investigator will maintain all study records according to ICH GCP and applicable regulatory requirements. Records will be retained for at least 2 years after the last marketing application approval or 2 years after formal discontinuation of the clinical development of the investigational product or according to applicable regulatory requirements. If the Investigator withdraws from the responsibility of keeping the study records, custody must be transferred to a person willing to accept the responsibility. DermBiont must be notified in writing if a custodial change occurs.

APPENDIX 1: SCHEDULE OF EVENTS

Evaluation or Task	Screen (- 28 day to day 1)	Day 1/ Baseline Prior to Application	Day 1/Day of application	*Day 2,3,4	Day 5	Day 14
		andres	Treat	eatment period		Follow up
Informed consent	X					
Demographics	X					
Inclusion/Exclusion	Х	X			3 4 -	
Ensure no use of soap and water on chest and back on previous day until scrub and culture samples are collected		x			x	х
Urine pregnancy test in women	X					X
Medical History	X	*	0			8
Concomitant Medication Query	X	X		Х	X	X
Clinical assessment of signs and symptoms of Tinea Versicolor (TV)	X	x	x	*X	X	X
Score signs and symptoms of local tolerability		X	x	*X	x	X
In-clinic KOH test (TV sites)	X					X
Bacterial culture all test sites		XΔ			XΔ	XΔ
Sample collection for molecular diagnosis (Scrub)		X			x	X
Record Adverse Events		X	X	*X	X	X
Application of Investigational Product (IP) ,aqueous gel and vehicle gel in the clinic (investigative site)			X	*X	x	
Instruct subject not to use soap and water on the chest and back for 12 hours after Day 1 IP ,aqueous and vehicle gel application. Use of soap and water on the chest and back is allowed on the mornings of Days 2, 3, and 4 for subjects in the multiple treatment dose groups.			X	*X		
Schedule appointment for next visit	x		x	*X	X	

*Only for subjects enrolled to receive multiple treatment doses on 5 consecutive days

Δ Not applicable to Cohort 4 subjects

Note: Screening and Day1/baseline can occur on the same day

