For each of the three DBI-002 probiotic cohorts, the single-treatment subjects (approximately 2) will be enrolled first. After every single-treatment subject has completed the Day 5 visit, local tolerability and adverse events (AEs) will be assessed. If there are no safety signals, enrollment of the cohort's multiple treatment subjects (approximately 4) will begin. After every multiple treatment subject has completed the Day 14 visit, local tolerability and adverse events (AEs) will be assessed. If there are no safety signals, enrollment of the next cohort will begin. Cohort 1 must be completed before enrolling Cohort 2. Cohort 2 must be completed before enrolling Cohort 3. If there are safety signals specific to local tolerability and AEs from either of the first two cohorts, the following dose escalating cohort may be not be enrolled if the Investigator and sponsor are in agreement.

Cohort 4 subjects will receive multiple treatments, Enrollment of Cohort 4 is independent of the three probiotic cohorts.

Study Flowchart

Visit 0 (may be combined with Visit 1): Screening and enrollment visit, KOH test of TV-affected chest and back skin locations

Visit 1: Baseline visit, Urine pregnancy test as applicable, clinical grading of signs and symptoms of TV, randomization of IP or aqueous gel to chest and back, scrub samples and samples for bacterial culture of IP and vehicle gel TV-affected anatomical locations prior to applications, application of IP and vehicle gel, adverse event recording

Visit 2: Clinical grading of signs and symptoms of TV, scrub samples and samples for bacterial culture of IP and aqueous gel TV-affected anatomical locations, clinical assessment of local tolerability, adverse event recording

Visit 3: Final study visit. Urine pregnancy test as applicable, clinical grading of signs and symptoms of TV, KOH test of TV-affected chest and back skin locations, scrub samples and samples for bacterial culture of IP and aqueous gel TV-affected anatomical locations, adverse event recording, standard-of-care TV treatment may be provided at the discretion of the Investigator

Subjects enrolled to the multiple treatment dose groups:

Visit 0 (may be combined with Visit 1): Screening and enrollment visit, KOH test of TV-affected chest and back skin locations

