Visit 1: Baseline visit, Urine pregnancy test as applicable, clinical grading of signs and symptoms of TV, randomization of IP or vehicle gel or aqueous gel to chest and back, scrub samples and samples for bacterial culture of IP, aqueous gel, and vehicle gel TV-affected anatomical locations prior to first applications, application of IP and vehicle gel, adverse event recording

Visits 2, 3, 4: Clinical grading of signs and symptoms of TV, application of IP, aqueous gel, or vehicle gel per randomization to TV-affected locations, clinical assessment of local tolerability, adverse event recording

Visit 5: Clinical grading of signs and symptoms of TV, scrub samples and samples for bacterial culture of IP, aqueous gel, and vehicle gel TV-affected anatomical locations prior to final applications, application of IP, aqueous gel, or vehicle gel, clinical assessment of local tolerability, adverse event recording

Visit 6: Final study visit. Urine pregnancy test as applicable, clinical grading of signs and symptoms of TV, KOH test of TV-affected chest and back skin locations, scrub samples and samples for bacterial culture of IP, vehicle gel, and aqueous gel TV-affected anatomical locations, adverse event recording, standard-of-care TV treatment may be provided at the discretion of the Investigator

1 2INTRODUCTION

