For each of the three probiotic cohorts, the single-treatment subjects (approximately 2) will be enrolled first. After every single-treatment subject has completed the Day 5 visit, local tolerability and adverse events (AEs) will be assessed. If there are no safety signals, enrollment of the cohort's multiple treatment subjects (approximately 4) will begin. After every multiple treatment subject has completed the Day 14 visit, local tolerability and adverse events (AEs) will be assessed. If there are no safety signals, enrollment the next cohort will begin. Cohort 1 must be completed before enrolling Cohort 2. Cohort 2 must be completed before enrolling Cohort 3. If there are safety signals specific to local tolerability and AEs from either of the first two cohorts, the following dose escalating cohort may be not be enrolled if the Investigator and sponsor are in agreement.

Cohort 4 subjects will receive multiple treatments, Enrollment of Cohort 4 is independent of the three probiotic cohorts, meaning that subjects may be enrolled before, in parallel with, or after the probiotic cohorts.

Subjects enrolled to the single-treatment dose groups:

Visit 0 (may be combined with Visit 1): Screening and enrollment visit, KOH test of TV-affected chest and back skin locations

Visit 1: Baseline visit, Urine pregnancy test as applicable, clinical grading of signs and symptoms of TV, randomization of IP or vehicle gel to chest and back, scrub samples and samples for bacterial culture of IP and aqueous gel TV-affected anatomical locations prior to applications, application of IP and aqueous gel, adverse event recording

Visit 2: Clinical grading of signs and symptoms of TV, scrub samples and samples for bacterial culture of IP and aqueous gel TV-affected anatomical locations, clinical assessment of local tolerability, adverse event recording

Visit 3: Final study visit. Urine pregnancy test as applicable, clinical grading of signs and symptoms of TV, KOH test of TV-affected chest and back skin locations, scrub samples and samples for bacterial culture of IP and aqueous gel TV-affected anatomical locations, adverse

event recording, standard-of-care TV treatment may be provided at the discretion of the Investigator

Subjects enrolled to the multiple treatment dose groups:

Visit 0 (may be combined with Visit 1): Screening and enrollment visit, urine pregnancy test as applicable, KOH test of TV-affected chest and back skin locations

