Visit 1: Baseline visit, clinical grading of signs and symptoms of TV, randomization of IP or vehicle gel to chest and back, scrub sample and bacterial culture of IP, aqueous gel, or vehicle gel TV-affected anatomical locations prior to first applications, application of IP, aqueous gel, or vehicle gel, adverse event recording

Visits 2, 3, 4: Clinical grading of signs and symptoms of TV, application of IP, aqueous gel, or vehicle gel per randomization to TV-affected locations, clinical assessment of local tolerability, adverse event recording

Visit 5: Clinical grading of signs and symptoms of TV, scrub sample and bacterial culture of IP, aqueous gel, or vehicle gel TV-affected anatomical locations prior to final applications, application of IP, aqueous gel, or vehicle gel, clinical assessment of local tolerability, adverse event recording

Visit 6: Final study visit. Urine pregnancy test as applicable, clinical grading of signs and symptoms of TV, KOH test of TV-affected chest and back skin locations, scrub sample and bacterial culture of IP, aqueous gel, and vehicle gel TV-affected anatomical locations, adverse event recording, standard-of-care TV treatment may be provided at the discretion of the Investigator

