6.5 Study Visits

The study will be conducted with:

- 1. A screening visit (Day -28 to Day 1),
- 2. Baseline visit (Day 1) for evaluation, sampling and treatment may be combined with the screening visit
- 3. Only for subjects enrolled to receive multiple treatment doses: Treatment and evaluation visits (Days 2, 3, 4)
- 4. Evaluation and sampling visit (Day 5), and treatment only for subjects enrolled to receive multiple treatments
- 5. Safety follow-up visit (Day 14)

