6.5.1 Screening Visit

Following written informed consent obtained from each subject, the Investigator will determine whether subjects are eligible to participate in the study by performing screening tests and evaluations.

Women of childbearing potential will be tested for pregnancy with a urine pregnancy test. Women who are pregnant or who have a positive pregnancy test will be excluded from the study.

(-28 Day to Day 1) Screening visit:

- 1. Informed consent.
- 2. Record demographics.
- 3. Review of Inclusion/Exclusion Criteria.
- 4. Ensure no use of soap and water on the chest and back within 12 hours before collection of Baseline scrub samples. Schedule the enrolled subject for Day 1 / Baseline visit if soap and water were used on the chest and/or back within 12 hours of the screening visit.
- 5. Women of childbearing potential will be tested for pregnancy with a urine pregnancy test.
- 6. Medical history.
- 7. Concomitant medication.
- 8. Clinical assessment of signs and symptoms of TV.
- 9. KOH test (TV-affected skin locations).

- 10. Record adverse event, if any.
- 11. If screening is not on the same day as all required Day / Baseline visit assessments and skin sampling, schedule an appointment for Day 1 / Baseline visit.

At the Screening visit, continuous monitoring of concomitant medications, therapies and AEs throughout the study period will begin.

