6.5.2 All Other Visits

Study visit assessments will be conducted as presented in Appendix 1. The Treatment Period for subjects receiving a single treatment dose is Day/Visit 1. The Treatment Period for subjects receiving multiple treatment doses is from Day/Visit 1 through Day/Visit 5.

Day 1/Baseline visit (before the IP is applied, the following tasks will have been completed):

- 1. Review of Inclusion/Exclusion Criteria.
- 2. Ensure no direct use of soap and water for at least 12 hours on the areas where the samples are to be collected on the chest and back. After sampling and application, instruct the subject not to use soap and water on the chest and back until the morning of the next day.
- 3. Concomitant medications.
- 4. Clinical assessment of signs and symptoms of TV.
- 5. Score the signs and symptoms of local tolerability of the areas affected by TV.
- 6. Collect scrub samples from each of the TV-affected skin locations to be treated with IP, aqueous gel, and vehicle gel.
- 7. After collecting each scrub sample, pat the sampling location dry with wipes.
- 8. Collect samples for bacterial culture of the IP and vehicle gel TV-affected skin locations. Not required for vehicle gel vs. aqueous gel subjects.
- 9. Assigned IP, aqueous gel, and vehicle gel will then be applied to designated locations on both anterior and posterior trunk (chest or back) by investigative site staff. Approximately 0.1-0.2 ml of the IP, vehicle gel, or aqueous gel will be applied to each selected location.
- 10. Record any adverse events.
- 11. Schedule an appointment for Day 5 for subjects receiving a single treatment dose and instruct the subject to not use soap and water on the chest and back for at least 12 hours before the Day 5 visit. Schedule an appointment for the next day for the Day 2 visit for subjects receiving multiple treatment doses.
- 12. Instruct the subject to not wash the treated locations with soap and water on the anterior and posterior trunk (chest or back) from the time of IP, vehicle gel, and aqueous gel application at the Baseline visit until the morning of the next day.

For subjects enrolled to receive multiple treatment doses only:

Day 2 / Visit 2, Day 3 / Visit 3, Day 4 / Visit 4:

- 1. Clinical assessment of signs and symptoms of TV.
- 2. Score the signs and symptoms of local tolerability of the locations affected by TV.

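### The protocol disagrees with itself on the pre-dose pregnancy test: three of four visit lists place it at Visit 1, but section 6.5 and Appendix 1 test only at screening (up to 28 days before dosing) and Day 14

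*Combined protocol and SAP*

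**What the plan says.** The timing of the pre-dose pregnancy test appears in several places.

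- **Synopsis, Study Flowchart, single-dose groups:** "Visit 1: Baseline visit, Urine pregnancy test as applicable, clinical grading of signs and symptoms of TV, randomization of IP or aqueous gel". The Visit 0 entry has no test.
- **Synopsis, Study Flowchart, multiple-dose groups:** "Visit 1: Baseline visit, Urine pregnancy test as applicable". Again there is none at Visit 0.
- **Section 4.1.1, single-dose groups:** test at Visit 1, none at Visit 0.
- **Section 4.1.1, multiple-dose groups:** "Visit 0 (may be combined with Visit 1): Screening and enrollment visit, urine pregnancy test as applicable". The next entry has no test: "Visit 1: Baseline visit, clinical grading of signs and symptoms of TV, randomization of IP or vehicle gel to chest and back".
- **Section 6.5.1:** women of childbearing potential are tested at screening, which section 6.5 allows from Day -28 to Day 1.
- **Section 6.5.2:** the 12-item Day 1 list contains no pregnancy test. The Day 14 list does.
- **Appendix 1:** the row "Urine pregnancy test in women" is marked under Screen and Day 14. Both Day 1 columns are blank.

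Section 6.5.2 opens with "Study visit assessments will be conducted as presented in Appendix 1". Combining screening with baseline is optional. Section 6.5.1, item 4, requires separate visits in one situation: "Schedule the enrolled subject for Day 1 / Baseline visit if soap and water were used on the chest and/or back within 12 hours".

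**The concern.** Pregnancy is exclusion criterion 1 in section 6.2. Eligibility is reviewed again on Day 1 before application, so the protocol means the criterion to hold at dosing. Without a test, that review cannot detect a pregnancy the woman does not know about. The eligibility criteria contain no contraception requirement; they only exclude women who plan a pregnancy.

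In Cohorts 1 to 3 the product is a live bacterium. Section 2.1 describes it as a reported opportunistic pathogen and accepts localised or systemic infection as possible, though unlikely. If the schedule table is followed, a woman whose pregnancy became detectable after screening could be dosed. If the synopsis is followed, she would be tested on Day 1 and excluded. The same woman could therefore be dosed or excluded depending on which part of the protocol the site uses.

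**Working it through.** **Step 1. Compare the places.**

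| Place | Visit 0 / screening | Visit 1 / Day 1 before dosing | Final visit |
|---|---|---|---|
| Synopsis flowchart, single dose | no | yes | yes |
| Synopsis flowchart, multiple dose | no | yes | yes |
| Section 4.1.1, single dose | no | yes | yes |
| Section 4.1.1, multiple dose | yes | no | yes |
| Sections 6.5.1 and 6.5.2 | yes | no | yes |
| Appendix 1 | yes | no | yes |

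The final-visit test is consistent throughout; the pre-dose test is not. Three of the four visit lists place it at Visit 1. For five-dose subjects the synopsis and section 4.1.1 contradict each other directly. The plain-text Day 1 list in section 6.5.2 agrees with the blank Day 1 cells in Appendix 1, so the blanks are not a table-reading fault.

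**Step 2. Age of the last negative test at dosing.** Inputs: a screening period of up to 28 days (section 4.1.1), five-dose treatment on Days 1 to 5, and final visit on Day 14 ± 2. All figures are upper limits for separate visits, with screening at the earliest permitted date.

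- To first dose under Appendix 1: 28 days. With a Day 1 test: 0 days.
- To last dose, five-dose subjects, under Appendix 1: 28 + (5 − 1) = 32 days. With a Day 1 test: 5 − 1 = 4 days.
- Between consecutive scheduled tests under Appendix 1: 28 + (14 − 1) ± 2 = 41 ± 2, that is 39 to 43 days. With a Day 1 test: 13 ± 2, that is 11 to 15 days.

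The 28 days is the period length the protocol states. If a Day 0 is counted between Day -1 and Day 1, as the synopsis visit description does, the span from Day -28 to Day 1 is 1 − (−28) = 29 days, and each Appendix 1 figure rises by one.

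**Step 3. Who could be affected.**

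- Live-organism subjects: 3 cohorts × 6 = 18, made up of 3 × 2 = 6 single-dose and 3 × 4 = 12 five-dose.
- Total: 18 + 4 = 22. The four Cohort 4 subjects receive no live organism.
- The documents do not say how many subjects will be women of childbearing potential, or how many will have separate visits. The number affected lies between 0 and 18 and cannot be narrowed.

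**The case against.** The case for treating this as a minor consistency note has several parts.

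- **No clause ranks Appendix 1 above the synopsis or section 4.1.1.** A site could satisfy every list by testing at screening and again at Visit 1. That is true, but section 6.5.2 sends the site to Appendix 1 for visit assessments, and a site working from that table does no Day 1 test.
- **Twenty-eight days is a ceiling.** The soap-and-water rule only forces a wait until a 12-hour wash-free interval is met, which could be the next day. The synopsis schedules single-dose screening on Day 0 and dosing on Day 1, a gap of one day. This stands: typical gaps may be much shorter. The protocol nevertheless permits up to 28 days with no repeat test.
- **The interval to the Day 14 test is secondary.** That test follows all dosing, so 39 to 43 days says how late a missed pregnancy might be found, not how well exclusion works. This also stands; the 28-day and 32-day figures are the relevant ones.
- **The range 0 to 18 is not an estimate.** Agreed. Its upper end would need every Cohort 1 to 3 subject to be a woman of childbearing potential with separate visits.
- **The hazard is modest and only partly visible.** Exposure is topical, section 2.1 ties reported infections mainly to hospital settings and immunocompromised hosts, and no pregnancy-specific hazard is described. Further precautions may sit in documents not seen here. A Day 1 test would also miss a very early pregnancy. These points limit the seriousness, but they do not reconcile the schedules or supply the missing test.

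**Conclusion.** The conflict is real. The schedule that section 6.5.2 tells sites to follow gives less protection than three of the four visit lists. With separate visits, it allows a first live-organism dose on a pregnancy test up to 28 days old, and a fifth dose on one up to 32 days old. With a Day 1 test these limits are 0 and 4 days. The figures assume screening at the earliest permitted date and no unscheduled repeat test. The gap is zero when screening and baseline fall on the same day.

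This is a subject-safety and consistency point that should be corrected. In Cohort 4 it concerns only consistent application of exclusion criterion 1. It does not touch the statistical analysis.

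**What to change.** 1. In Appendix 1, mark the urine pregnancy test in the Day 1/Baseline column that precedes application, for women of childbearing potential, required whenever screening took place on an earlier day.
2. Add the same item to the Day 1 pre-application list in section 6.5.2.
3. Keep the screening and Day 14 tests.
4. Align both synopsis flowcharts and both section 4.1.1 visit lists with this schedule: a test at Visit 0, a repeat at Visit 1 if that is a later day, and the final-visit test unchanged.

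The cost is wording, plus at most one additional urine test per affected woman. Three of the four visit lists already call for a test at that visit. A single schedule would also spare sites a deviation from one section for following another.
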